3.2.3 Exploratory endpoints/outcomes

(o) Changes in HS CRP over 96 weeks with evaluation at week 24, 48 and 96.

3.3 Derived variables

The following derived variables will be studied:

Variables	Calculation method
Age at inclusion, years	Difference between the date of enrolment and the birth date divided by 365.25
CD4/CD8 ratio	CD4 cell count divided by CD8 cell count
Duration on ART, years	Difference between the date of enrolment and the date of first antiretroviral treatment initiation divided by 365.25
Time since HIV diagnosis, years	Difference between the date of enrolment and the date of HIV diagnosis divided by 365.25
Duration of suppressed HIV RNA (<50 copies/mL), year	Difference between the date of enrolment and the date of last detectable viral load (HIV RNA >50 copies/mL) divided by 365.25
Changes from baseline in continuous biological parameters	Difference between value at each time point and the value at baseline
Percent change from baseline in continuous biological parameters	Difference between value at each time point and the value at baseline divided by the baseline value and multiply by 100
Number of potential DDIs avoided	Difference between number of interactions graded "amber or red" before switching and number of interactions graded "amber or red" after switching to dolutegravir/rilpivirine
Total cell associated HIV DNA copies per million PBMC	Total cell associated HIV DNA will be analysed as log transformed, as a continuous variable

[figure not shown]
Partial dates will be extrapolated. For example, all dates saved as NK/FEB/2020 will be recoded as 15/FEB/2020 and those saved NK/NK/2020 will be recoded as 15/JUNE/2020. NK means not known.

4. Study Methods

4.1 General Study Design and Plan

This trial is an open-label, randomised, 2 arms, parallel-group, multicentre trial, comparing an immediate versus a deferred switch from a boosted PI containing regimen to a dual therapy with DTG and RPV in HIV infected patients with a history of virological failure with NNRTIs or baseline transmitted drug resistance and having developed a K103N mutation. The trial will be conducted within the NEAT ID network and include sites in 7 countries that have an excellent track record in clinical research. After screening, participants will be randomised 2:1 to switch to DTG/RPV at baseline or at 48 weeks.

The intervention will consist of immediate switch to DTG 50 mg OD + RPV 25 mg OD regimen at baseline or maintaining the current antiretroviral therapy for 48 weeks. At week 48, all participants in the deferred switch group with virological success will be switched to DTG 50 mg OD + RPV 25 mg OD therapy, and all participants will be followed for additional 48-weeks until week 96 (see figure).

After the screening visit, participants will be seen at baseline, weeks 4, 12, 24, 48, 52, 60, 72, 96, and either a follow-up visit (30 days (+/- 7 days) after week 96 visit) or an early termination visit. A week 60 visit may be an optional visit and performed for subjects on the control arm (3 months after therapeutic modification) as required per national guidelines. At each visit, participants will have routine investigations and will include viral load, CD4 & CD8, haematology (including haemoglobin, white cell count and differential, platelets), biochemistry (including sodium, potassium, creatinine, albumin, glucose, ALT, AST, ALP, total bilirubin, total cholesterol, HDL, LDL, triglycerides), PK, PBMC, quality of life questionnaires, patient satisfaction questionnaire, Pittsburgh sleep questionnaire, DDI assessment & urine sample (for haematuria, proteinuria, glycosuria, leukocytes) for full list of investigations please see section 4.4.

Statistical Analysis Plan

WISARD Study Protocol

Haematology Including:
 
 • Platelet count • RBC Count (indices MCV & MCH) • WBC count (absolute) • Haemoglobin • Hamatocrit RBC 
Count indices:
 
 • MCV • MCH 
Automated WBC differentials:
 
 • Neutrophils • Lymphocytes • Monocytes • Eosinophils • Basophils 	x	x	x	x	x	x	x	x	x	

Clinical chemistry (Fasted for at least 10 hours except for screening) Including:
 
 • Urea • Chloride • Alkaline phosphatase • Creatine phosphokinase • Creatinine • Calcium • Phosphate • Glucose (optional in 	x*	x*	x	x	x*	x*	x	x	x	x

urine if agreed with sponsor in writing)
 
 • Total bilirubin • Potassium • HsCRP (optional if agreed with sponsor in writing) • Total protein • Sodium • ALT • Albumin • Creatinine clearance (Calculations: Cockcroft-Gault (requires weight), MDRD, CKD-Epi) 
(* including urinary chemistry)
										

Statistical Analysis Plan

WISARD Study Protocol

Fasting Lipids (Fasted for at least 10 hours except at screening) Including: • Total cholesterol • HDL cholesterol • LDL cholesterol • Triglycerides	x	x	x	x	x	x	x	x	x	x	x	x	
HIV RNA viral load		x	x	x	x	x	x	x	x	x		x	
Predose Pharmacokinetic assessment (A post-dose sample will be taken at early termination visit and/or in the event of virological failure within 20-28 hours of last dose)			x (Experimental arm only)				x (Experimental arm only)				x		x
Blood sampling for PBMC isolation (Required unless exemption documented in site contract i.e. if site does not have capacity to process PBMC samples)		x					x				x		x
Quality of Life Questionnaire		x			x	x					x		x
Patient Treatment Satisfaction Questionnaire		x			x	x					x		x
Pittsburgh Sleep Questionnaire		x			x	x					x		x
DDI Assessment		x			x	x					x		x
Adherence Assessment (Self report at visit) (including date and time of last dose on PK days, including ETV visit and/or in the event of virological failure)		x	x	x	x	x	x	x	x	x			x
AE Assessment		x	x	x	x	x	x	x	x	x	x		x
Con Med Check	x	x	x	x	x	x	x	x	x	x			x

5. Sample Size calculation

This is a pilot proof of concept study to investigate whether complex regimens taken by patients with resistance mutations can be replaced by a simple two class single pill regimen safely in terms of viral load and adverse events.

No formal sample size calculation is performed. It is anticipated that data from 150 participants is adequate to meet the trial objectives (100 in the DTG/RPV arm and 50 in the control arm). The expected success rate is 95% based on the data reported by the SWORD 1 & 2 studies (1). If the observed success rate is 95% in the DTG/RPV arm at week 48 and varies from 95% to 100% in the

Statistical Analysis Plan

WISARD Study Protocol

control arm, with 150 participants (100 in the DTG/RPV arm and 50 in the control arm), the lower bound of the confidence interval of the difference in the success rate between the 2 arms (DTG/RPV – control) would varied from -9.3% to -7.4% (see table below).

Success rate			95% Confidence Interval	
DTG/RPV (n=100)	Control (n=50)	Difference	lower	upper
95%	95%	0.0%	-7.4%	7.4%
95%	96%	-1.0%	-7.9%	5.9%
95%	97%	-2.0%	-8.4%	4.4%
95%	98%	-3.0%	-8.8%	2.8%
95%	99%	-4.0%	-9.1%	1.1%
95%	100%	-5.0%	-9.3%	-0.1%

In addition, we would like to show whether the observed success rate in the DTG/RPV arm is above 95%. Therefore, we estimated power for a one-sample proportion test (Binomial test) by varying the external threshold from 80% to 90% to detect the minimum effect size at which we will have 80% power to achieve the goal (see table below).

Ho (null hypothesis): $p = p_0$ versus Ha (alternative hypothesis): $p > p_0$

N	alpha	p	p0	delta	power
100	5%	95%	80%	15%	100%
100	5%	95%	81%	14%	99.9%
100	5%	95%	82%	13%	99.6%
100	5%	95%	83%	12%	98.9%
100	5%	95%	84%	11%	97.2%
100	5%	95%	85%	10%	93.7%
100	5%	95%	86%	9%	93.7%
100	5%	95%	87%	8%	87.2%
100	5%	95%	88%	7%	76.6%
100	5%	95%	89%	6%	61.6%
100	5%	95%	90%	5%	43.6%

We show that, with 100 individuals in the DTG/RPV arm, we will have a 95% probability to discard a combination for which efficacy is smaller than 87% and we will select with a power of 80% the strategy for which the efficacy is above or equal to 95%.

The power calculation was made using the statistical software package nQuery Advanced, using the exact test for single proportion module (Version 8.5.2.0).

An interim analysis will be performed when 120 participants will reach the week 24 visit (corresponding to 80 participants in the DTG/RPV arm and 40 participants in the control arm). In the ANRS 163 ETRAL trial (Katlama et al., JAC 2019)(2), in which 10% of participants harboured viruses with K103N mutation, the proportion of participants in success at week 24 with a dual therapy with etravirine and raltegravir was estimated at 96.4% (95%CI 92.3 to 98.7). Therefore, for this interim analysis at week 24: The expected level of efficacy is 96%, and the unacceptable level of efficacy (p_0) is 87%. With $\alpha = 5\%$ (one-sided) and 80% power, if we include 80 participants in the DTG/RPV arm, we will consider that the treatment is effective to be continued if there are no more than 4 failures. We test the null hypothesis $H_0: p \leq 87\%$ versus the alternative hypothesis $H_a: p \geq 96\%$, with an 80% chance that the lower bound of the 95% confidence interval would exclude 87% if the true success rate (p) is 96%. This gives a 5% chance of continuing if $p = p_0$ and an 80% chance of continuing if $p \geq 96$.

6. General Considerations

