6.8 Multiple testing

As only an administrative interim analysis will be conducted, no multiplicity adjustment is required.

[figure not shown]
7. Summary of Study Data

All continuous variables will be summarized using the following descriptive statistics: n (non-missing sample size), mean, standard deviation, 1st quartile, median, 3rd quartile, maximum and minimum. The frequency and percentages (based on the non-missing sample size) of observed levels will be reported for all categorical variables.

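### The week-48 power is for a single look; if the week-24 rule of at most 4 failures in 80 is binding, it falls from 87.2% to about 75%, and the plan does not settle whether that rule binds

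*SAP*

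**What the plan says.** **Week-48 power.** SAP section 5 and Protocol 9.1 carry the same text. "The expected success rate is 95% based on the data reported by the SWORD 1 & 2 studies". A table gives one-sample power for 100 participants at thresholds from 80% to 90%, calculated "using the exact test for single proportion module". The row for the 87% threshold reads "100 5% 95% 87% 8% 87.2" (N, alpha, true rate, threshold, difference, power, in per cent). The summary sentence below the table promises that "we will select with a power of 80% the strategy for which the efficacy is above or equal to 95" per cent.

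**Week-24 look.** SAP section 5 and Protocol 9.5 add an interim analysis at 120 participants, "corresponding to 80 participants in the DTG/RPV arm and 40 participants in the control arm". "The expected level of efficacy is 96%, and the unacceptable level of efficacy" is 87%. The rule is: "we will consider that the treatment is effective to be continued if there are no more than 4 failures". Both documents state an 80% chance of continuing at 96%.

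**Other passages on the same look.** SAP 6.6 calls it administrative. It rates the strategy acceptable if the lower 95% limit exceeds 87%, and unacceptable at 18 or more failures. SAP 6.8 states: "As only an administrative interim analysis will be conducted, no multiplicity adjustment is required". Protocol 9.6 bases stopping on efficacy and safety evaluated together.

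**The concern.** To be selected at week 48, a regimen must first be continued at week 24. Neither document combines the two steps. SAP section 5 gives the interim hypotheses, an error rate, a power and a chance of continuing, which are the operating characteristics of a go/no-go decision. Yet the week-48 power is quoted as if no such decision came before it.

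If the rule is followed, a regimen that performs exactly as hoped has a materially lower chance of being selected than the power sentence implies. A monitoring board that sees 5 failures in 80 (93.75% success) would be outside the cut in SAP section 5 and far from the 18 failures in SAP 6.6. The plan tells it neither which rule applies nor what acting on the first one costs.

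**Working it through.** **Inputs**
- Week 48: n = 100, true success 95%, threshold 87%, one-sided exact test at 5% (SAP section 5, Protocol 9.1).
- Week 24: n = 80, expected success 96%, continue if failures ≤ 4 (SAP section 5, Protocol 9.5).
- Assumption: a week-24 failure is also a week-48 failure. SAP 8.1 supports this, since success requires suppression up to week 48 with no discontinuation.
- Assumption: the 80 participants seen at week 24 are among the 100 seen at week 48, and the same analysis population is used at both looks.

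**Step 1: reproduce the plan's figure.** At 87% success, P(≤ 7 failures in 100) = 4.31% and P(≤ 8) = 8.45%, so the one-sided 5% test passes with at most 7 failures. At 95% success, P(≤ 7 failures in 100) = 87.2%, which matches the table.

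**Step 2: chance of continuing.** With X ~ Bin(80, 0.04), P(X ≤ 4) = 78.4%, so the chance of not continuing is 21.6%. The plan rounds the first figure to 80%.

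**Step 3: both looks.** Of the 80, those not failed by week 24 fail by week 48 with probability (0.05 − 0.04)/0.96 = 0.0104. The other 20 fail with probability 0.05. For each X, the table gives the chance that total failures stay at or below 7.

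| X at week 24 | P(X) | P(total ≤ 7 given X) | Product |
|---|---|---|---|
| 0 | 0.0382 | 0.9995 | 0.0381 |
| 1 | 0.1272 | 0.9978 | 0.1269 |
| 2 | 0.2094 | 0.9906 | 0.2074 |
| 3 | 0.2268 | 0.9660 | 0.2191 |
| 4 | 0.1819 | 0.8959 | 0.1630 |
| Sum | 0.784 | | 0.755 |

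The probability of continuing and passing is 75.5%. The cost of a binding rule is 87.2 − 75.5 = 11.7 points.

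**Step 4: sensitivity to the week-24 rate, with week 48 held at 95%**

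| Week-24 success | Continue | Continue and pass (≤ 7/100) |
|---|---|---|
| 95% | 62.9% | 62.5% |
| 96% | 78.4% | 75.5% |
| 97% | 90.7% | 83.4% |

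**Step 5: the rule in SAP 6.6.** If only 18 or more failures in 80 stop the trial, the chance of stopping at 96% success is below 0.0001. Power stays at 87.2%.

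**Step 6: a different week-48 criterion.** Suppose week 48 were judged by an exact two-sided 95% interval with its lower limit above 87%. The limit is 87.4% for 94/100 and 86.1% for 93/100, so at most 6 failures pass. Power is then 76.6% without the interim and 70.3% with it. With a Wald interval, 93/100 has a lower limit of 88.0% and 92/100 has 86.7%. Seven failures still pass, and the joint figure returns to 75.5%.

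**Step 7: false selection.** At 87% success at both times, the chance of passing is 4.3% on the single look and 1.3% if both looks must be passed. The interim allows no early claim of success, so it does not inflate the error of the week-48 test.

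**The case against.** The strongest objection is that the documents do not establish the 4-in-80 cut as a binding stop. SAP 6.6, the section devoted to the interim, sets its unfavourable label at 18 failures and gives no action for 5 to 17. Protocol 9.6 calls for a combined evaluation, and Protocol 6.20 refers stopping criteria to the board's charter. This stands. A reader might infer that the plan will stop about one fully effective trial in five. That follows from SAP section 5 and Protocol 9.5 taken alone, but not from the documents together. It does not remove the point, because those two sections do state a continue rule, and SAP 6.6 itself reserves its acceptable label for a lower limit above 87%. With an exact interval that is again at most 4 failures (76/80 gives 87.7%, 75/80 gives 86.0%).

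A reader might also infer that power is about 70% with the planned interval. SAP 8.1 plans a two-sided 95% interval per arm, but names no method for it and attaches no 87% criterion. Exact limits are named only for secondary endpoints. Even on that reading, power is 76.6% before any interim, so the interim accounts for about 6 points and the change of criterion for the rest.

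The size is also fragile. At the 96.4% observed in the cited raltegravir–etravirine study, which the plan rounds to 96%, the joint figure is 79.3%. Protocol 9.5 specifies the per-protocol population for the interim and SAP 6.6 the modified intention-to-treat population. A participant counted as a non-success at week 24 only for missing data could be a success at week 48. Finally, this is a declared pilot with no formal sample-size calculation, which limits the consequence, although the power statement is still made.

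**Conclusion.** The point holds conditionally. If the continue rule in SAP section 5 and Protocol 9.5 is acted on, the probability of selecting a regimen with 96% success at week 24 and 95% at week 48 is about 75%, against 87.2% in the table and 80% in the sentence. That rests on the persistence and same-population assumptions above, and a week-24 rate one point higher or lower moves it widely. If the rule is not acted on, the quoted power is correct for the test described.

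What holds without condition is that SAP section 5 and Protocol 9.5 conflict with SAP 6.6 on what the interim decides, and that no passage says which reading the power statement assumes. The conclusion in SAP 6.8 that no multiplicity adjustment is needed is not disturbed. Only its stated reason, that the look is administrative, fails if the cut is binding.

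**What to change.** Reconcile SAP section 5 and Protocol 9.5 with SAP 6.6, SAP 6.8 and Protocol 9.6 on whether the 4-in-80 cut is binding, and cover the range of 5 to 17 failures. Which rule should apply is for the sponsor and the monitoring board.

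- **If binding:** in SAP section 5 and Protocol 9.1, restate power as the probability of passing both looks (about 75%), with the assumed rates, the persistence assumption, the population and the range from 62.5% to 83.4%. Drop the word administrative from SAP 6.6 and 6.8, and base the multiplicity statement on the absence of any early claim of success.
- **If advisory:** say so, and state that the quoted power assumes that the cut is not acted on.

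In either case, state the criterion and interval method that define success at week 48, since the figure depends on them. The cost is a few sentences in two documents and, if the cut is binding, a less favourable stated power. Sample size, error rate and analyses are unchanged.

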6.1 Timing of Analyses

An interim analysis will be performed to show whether DTG/RPV is able to maintain virological suppression at week 24, when 80% of the total participants will reach the 24-week visit (i.e. 120 participants: 80 in the DTG/RPV arm and 40 in the control arm) (anticipated to be November 2020).

The primary efficacy analysis will be performed at week 48, when all enrolled participants will reach the 48-week visit (anticipated to be May 2021).

The final analysis will be performed at week 96, when the last patient has completed his last scheduled visit in the protocol and when the database will be frozen (anticipated to be June 2022).

6.2 Timing of outcome assessments

Visit	Window (Through End-of-Study Week)	Window (Days)
12	6-18	43-126
24	18-30	127-210
48	42-54	295-378
72	66-78	463-546
96	90-102	631-714

6.3 Analysis Populations

6.3.1 Full Analysis Population

All randomly assigned participants will be included in the Full Analysis Population, except those who never received the study treatment. The participants who never received the study treatment will be excluded from the analysis. The primary endpoint and all secondary endpoints will be analysed on this Full Analysis population, called as a modified intention-to-treat (mITT) analysis.

6.3.2 Per-Protocol Population

The per-protocol population will include all patients from the mITT population, excluding participants with serious protocol violations which could interfere with the reliability of the efficacy outcome. Examples would include taking other antiretroviral treatment during the course of the study, incorrect randomisation or early discontinuation from the study for reasons unconnected to efficacy or safety. This analysis will be conducted to check the reliability of the results from the primary efficacy analysis.

6.3.3 Switch Included Population

In addition, a “Switch Included” analysis will be conducted, to check the outcomes of participants who discontinued randomised treatment for any reason. This analysis will follow the same methods as FDA Snapshot, but will include HIV RNA data from all participants with results available at Week 48, whether they are on or off randomised treatment. There will be no formal non inferiority outcome analysis as this is a pilot study.

6.3.4 Safety Population

The safety population will include all subjects included in the mITT population who received at least one dose of the study treatment

6.4 Covariates and Subgroups

6.4.1 Subgroup analysis

The sample size of 150 patients is too small to allow meaningful subgroup analyses. The two analyses described above (Per Protocol and Switch Included) will assess the reliability of the results from the primary efficacy analysis.

6.4.2 Adjusted analysis

The treatment effect will also be assessed adjusted for baseline variables which might influence the 48-week outcome.

Factors associated with the outcome will be tested using univariable logistic regression models. The following baseline variables will be tested: Age, gender, ethnic (black vs white), transmission group (MSM vs Other), Known duration since HIV diagnosis, duration of ART therapy, Positive Hep B antigen (yes vs no), Positive Hep C antibody (yes vs no), CD4 (above versus below 350 cells/ μ L), CD4/CD8 ratio, NRTI-backbone, PI received at baseline (yes vs no), body mass index, alcohol intake (yes vs no), current smoking (yes vs no), recreational drug use (yes vs no), diabetes (yes vs no), metabolic parameters (LDL-c, HDL-c, total cholesterol (TC), triglycerides and TC/HDL ratio), glucose, total protein, hsCRP, Creatinine clearance (e-GFR), presence of M184V mutation at baseline (yes vs no), number of PI mutation, number of NRTI mutation and number of allowed NNRTI mutation. Continuous variables will be modelled as continuous or as tertiles based on the AIC of the corresponding univariable model. Variables with univariable p-value <0.10 will be retained for the multivariable analysis.

All potential confounders that are known in the literature will also be included, such as the presence of M184V mutation at baseline and CD4 count at baseline (above versus below 350 cells/ μ L).

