 - St John's wort (*Hypericum perforatum*).
13. Has acute viral hepatitis including, but not limited to, A, B, or C.
14. Active hepatitis B/ Hep B non-immune subjects who have failed vaccination (antibody concentration < 10 international units). (If local practice does not include vaccination of low risk patients, then the patients without HBsAb are not excluded – this must be clearly documented in the medical records and eCRF). Note: subjects can be re screened if they receive vaccination and subsequently meet eligibility criteria.
15. Evidence of Hepatitis B virus (HBV) infection based on the results of testing at Screening for Hepatitis B surface antigen (HBsAg), Hepatitis B core antibody (anti-HBc), and Hepatitis B surface antibody (HBsAb)

CONFIDENTIAL

as follows: Participants positive for HBsAg are excluded; Participants positive for anti-HBc (negative HBsAg status) and negative for HBsAb are excluded (if local practice does not include vaccination of low risk patients, then the patients without HBsAb are not excluded – this must be clearly documented in the medical records and eCRF). Note: Subject positive for anti-HBc (negative HBsAg status) and positive for HBsAb are immune to HBV and are not excluded.

16. Participants with an anticipated need for any Hepatitis C virus (HCV) therapy during the Early Switch Phase and for interferon-based therapy for HCV throughout the entire study period.
17. Any investigational drug within 30 days prior to the trial drug administration.
18. Any evidence of viral resistance different to the one described in the inclusion criteria i.e. not meeting inclusion criteria or having different mutation at K103.
19. Dialysis or renal insufficiency (creatinine clearance < 50ml/min).
20. History of decompensated liver disease (Alanine aminotransferase (ALT) \geq 5 times the upper limit of normal (ULN), OR ALT \geq 3xULN and bilirubin \geq 1.5xULN (with >35% direct bilirubin).
21. Unstable liver disease (as defined by the presence of ascites, encephalopathy, coagulopathy, hypoalbuminemia, esophageal or gastric varices, or persistent jaundice), cirrhosis, known biliary abnormalities (with the exception of Gilbert's syndrome or asymptomatic gallstones).
22. Subjects with severe hepatic impairment (Class C) as determined by Child-Pugh classification (see appendix 4).
23. Opportunistic infection within 4 weeks prior to first dose of DTG plus RPV.
24. Clinical decision that a switch of antiretroviral therapy should be immediate.

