9.4 Adjusted analysis

The primary efficacy analysis will be by multiple logistic regression. This analysis will be adjusted for two baseline categorical variables which might influence the 48-week outcome: presence of M184V mutation at baseline and CD4 count at baseline (above versus below 350 cells/UI).

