8.1 Primary Efficacy Analysis

Virologic outcome will be determined by the last available measurement while the participant is on treatment and continued on trial within the time window (see Table A, section 6.2).

The primary efficacy analysis will be performed at week 48 with the mITT population. The proportion of patients with treatment success will be estimated by the number of patients with HIV-RNA<50 copies/mL up to week 48 with no discontinuation of the study or the study treatment at week 48 divided by the total number of participants in the mITT population. The associated two-sided 95% confidence interval will be calculated for each treatment group. We will also calculate the difference in treatment efficacy between the two treatment groups by measuring the difference in the percentage of participants with therapeutic success (i.e., DTG/RPV success rate minus the control success rate). The two-sided 95% confidence interval of the difference in therapeutic success rate will be given by the following formula (A):

$$(\hat{p}_1 - \hat{p}_2) \pm 1.96 \sqrt{\frac{\hat{p}_1 \hat{q}_1}{n_1} + \frac{\hat{p}_2 \hat{q}_2}{n_2}} \quad \text{where } \hat{q} = 1 - \hat{p}$$

The effect of study treatment will also be assessed in the mITT population using logistic regression model with treatment group adjusted for the presence of M184V mutation at baseline and CD4 count at baseline (above versus below 350 cells/ μ L) as well as all baseline variables potentially associated with the outcome, with univariable P-value <0.10 as described above in the section 6.4.2.

Sensitivity analyses will be performed with both the per-protocol and the switch included populations.

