8.2.1 Virological evaluation

(a) Proportion of participants with virological failure (2 consecutive VL >50 copies/mL or one VL >50 copies/mL and discontinuation of the study or the study treatment) over 96 weeks

The Kaplan-Meier estimates will be used to determine the proportion of participants with virologic failure, investigated over the 96 weeks. The associated two-sided 95% confidence interval will be calculated for each group with Kalbfleisch and Prentice's formula. The Log-Rank test will be used to compare the virological failure rate between the 2 groups. An additional analysis using Cox regression model with treatment group adjusted for the presence of M184V mutation at baseline and CD4 count at baseline (above versus below 350 cells/ μ L) as well as all other potential confounders will be used to assess the effect of study treatment. We will also calculate the two-sided 95% confidence interval of the difference in the percentage of participants with virological failure (i.e., DTG/RPV failure rate minus the control failure rate) using the following formula (B):

$(\hat{p}_1 - \hat{p}_2) \pm 1.96 \sqrt{\hat{s}_1^2 - \hat{s}_2^2}$ where \hat{s} is the standard error of the proportion calculated with the Kaplan-Meier Method based on the Greenwood pointwise variance estimate.

The time from randomisation to virological failure is defined as the date of the first occurrence of virological failure or the date of last observation for participants without virological failure minus the date of initiating the study treatment. The date of virological failure is the date of the first of the 2 measurements conferring virological failure. The event will be the occurrence of virological failure. Participants in discontinuation for reasons other than virological failure will be censored at the date of last observation before evaluation.

(b) Incidence of genotypic resistance in case of confirmed HIV RNA >50 and baseline factors associated with failure i.e. treatment emergent mutations (NRTI, NNRTI, PI and II regions) as compared with previous resistance tests.

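### The adjusted week-48 model picks covariates by p<0.10 from 30 candidates on about 5 to 7.5 expected failures, and the protocol and SAP disagree on whether that model is primary

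*SAP*

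**What the plan says.** Protocol 9.4 states that the primary efficacy analysis is a multiple logistic regression and fixes its covariates: "This analysis will be adjusted for two baseline categorical variables which might influence the 48-week outcome". These are M184V and CD4 cut at 350.

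SAP 8.1 is ordered differently. It gives the success proportion in each arm, then the unadjusted difference with an interval from formula (A), and only then says that a logistic model will also be used. That model holds treatment, M184V and CD4, "as well as all baseline variables potentially associated with the outcome, with univariable P-value <0.10".

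SAP 6.4.2 supplies the selection rule. Each listed baseline variable is tested in its own logistic model, and AIC decides whether a continuous variable enters as linear or as tertiles. Then: "Variables with univariable p-value <0.10 will be retained for the multivariable analysis". The section also brings in any confounder known from the literature, with M184V and CD4 given only as examples.

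The Cox model for virological failure in SAP 8.2.1(a) has a similar open clause: M184V and CD4, "as well as all other potential confounders will be used to assess the effect of study treatment".

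The SAP sets no cap on the number of covariates, no rule for collinear candidates and no fallback if a model separates.

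**The concern.** The planned trial has very few failures to model. Screening many variables at a loose threshold on so few events lets in variables that are associated with failure by chance, and each one takes up information needed for the treatment effect. Randomisation already prevents systematic confounding, so the screen is not needed for a valid comparison.

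The result also depends on choices that are not written down. The SAP does not say whether the screening p-value is Wald or likelihood ratio, and SAP section 13 assigns no software to logistic or Cox regression, so no default can be inferred. The literature clause has no list. In an open-label trial, these are choices that can be made after outcomes are known.

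The candidate list has weaknesses of its own. Total cholesterol, HDL and their ratio are functionally linked. Hepatitis B antigen should be constant, because under Protocol 5.2 "Participants positive for HBsAg are excluded". Ethnicity is coded black versus white with no category for anyone else.

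At stake is the adjusted treatment effect, which Protocol 9.4 calls primary.

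**Working it through.** **Inputs from the documents**
- Success: "The expected success rate is 95% based on the data reported by the SWORD 1 & 2 studies" (Protocol 9.1; SAP section 5). The planning table lets control success run from 95% to 100%.
- Size: "100 in the DTG/RPV arm and 50 in the control arm".
- Loss to follow-up: 15%, time point not given (Protocol 6.12). Missing data count against success (Protocol 9.8; SAP 6.5).
- Candidates in SAP 6.4.2: 30, counting the five metabolic parameters separately; 28 besides M184V and CD4; 27 if hepatitis B antigen is left out as constant.

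**Assumptions not in the documents:** no true covariate effects; M184V prevalence 50% (40% in a second simulation); CD4 below 350 in 15%.

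**Step 1. The plan's own figure.** Formula (A) at 95% versus 95%: 1.96 × √(0.95×0.05/100 + 0.95×0.05/50) = 1.96 × 0.0377 = 7.4 points. This reproduces the stated lower bound of -7.4%. The other five lower bounds also reproduce (-7.9, -8.4, -8.8, -9.1, -9.3).

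**Step 2. Expected failures.** 100(1 - pE) + 50(1 - pC):
- 95%/95%: 5 + 2.5 = 7.5
- 95%/98%: 5 + 1 = 6
- 95%/100%: 5 + 0 = 5
- all of the 15% loss counted as failure by week 48: 150 × (1 - 0.95×0.85) = 28.9

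**Step 3. Simple count.** 28 candidates × 0.10 = 2.8 retained by chance; P(at least one) = 1 - 0.9^28 = 0.95, treating candidates as independent. With treatment, M184V and CD4 that is about 6 parameters: 7.5/6 = 1.25 failures per parameter, or 5/6 = 0.83. The two-covariate model has 3 parameters: 7.5/3 = 2.5, or 5/3 = 1.7.

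**Step 4. Simulation of the SAP rule.** 150 patients, 27 noise candidates, M184V and CD4 forced in, AIC choice of linear or tertile, p<0.10. Separation means that some coefficient is infinite.

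| Success, DTG/RPV and control | Screening test | Mean failures | Noise variables added | Median failures per parameter | Separation, screened model | Separation, two covariates |
|---|---|---|---|---|---|---|
| 95%, 95% | Wald | 7.6 | 1.9 | 1.50 | 37% | 36% |
| 95%, 95% | LR | 7.5 | 4.3 | 0.78 | 86% | 35% |
| 95%, 98% | Wald | 6.2 | 1.7 | 1.33 | 59% | 59% |
| 95%, 98% | LR | 6.2 | 4.3 | 0.67 | 95% | 62% |
| 90%, 90% | Wald | 15.2 | 2.8 | 2.35 | 9% | 9% |
| 90%, 90% | LR | 15.1 | 4.0 | 1.80 | 48% | 11% |
| 80.75%, 80.75% | Wald | 28.2 | 3.4 | 3.81 | 1% | 1% |
| 80.75%, 80.75% | LR | 28.8 | 3.9 | 3.43 | 10% | 2% |

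There were 600 runs in the first three rows (standard error at most √(0.25/600) = 2.0 points) and 200 in the others (at most 3.5 points). A second simulation of 1,300 trials at 95%/95%, with M184V at 40%, gave 1.9 (Wald) and 4.4 (LR) noise variables and 39% separation with two covariates.

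**Step 5. Why two covariates already separate.** With 15% below 350 there are about 22 such participants, and P(no failure among them) = 0.95^22 = 32%. P(no control failure) = 0.95^50 = 7.7%. Treated as independent: 1 - 0.676 × 0.923 = 38%, in line with the simulated 35-39%. The treatment odds ratio has no finite value whenever the control arm has no failures: 7.7% of trials at 95% control success, 0.98^50 = 36% at 98%, and always at 100%.

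**The case against.** The strongest reply is that the main result does not rest on this model. SAP 8.1 gives the unadjusted difference first, the planning table concerns "the lower bound of the confidence interval of the difference in the success rate between the 2 arms" without adjustment, and the interim criteria in SAP 6.6 use unadjusted proportions and differences. Protocol 9.2.2 describes a comparison of percentages in a pilot study and leaves the details to the SAP. This stands, and it limits the damage to the adjusted estimate. It does not explain why Protocol 9.4 calls the logistic model primary.

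Second, a reader might infer that the SAP overrides the protocol's covariates. It does not: M184V and CD4 are forced into the model. The conflict lies in the added, data-selected set and in the model's status.

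Third, a reader might infer that screening usually makes the model inestimable. That depends on the unstated test. Under Wald screening, separation is about the same as with two covariates (37% against 36%), because sparse failures are the cause. Under likelihood-ratio screening it rises to 86%. With failures near 29 it falls to 1-10%. Overfitting persists throughout; frequent inestimability does not.

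Fourth, a constant hepatitis B variable would simply drop out, and the candidate list, threshold and AIC rule are written down. That is fair. What cannot be reproduced from the text is the screening test and the literature set.

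**Conclusion.** The concern holds for the adjusted treatment estimate. At the documents' planning rate there are about 5 to 7.5 failures. The SAP rule adds about 2 to 4 pure-noise variables and leaves about 0.8 to 1.5 failures per parameter at 95% success in both arms. The ratio stays below 4 up to about 29 failures. The estimate is overfitted and depends on unstated choices.

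Two limits apply. The formula (A) difference is untouched, so the documents do not support reading this as a flaw in the trial's unadjusted result. And fixing the covariates does not by itself cure sparse data: about 36-39% of simulated trials have an infinite coefficient with only the two protocol covariates.

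The failure counts rest on the plan's 95% success and, at the upper end, on all of the 15% loss counting as failure by week 48. The separation rates also rest on the assumed M184V and CD4 prevalences. The disagreement over which analysis is primary is a matter of text and needs no assumption.

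**What to change.** - In SAP 6.4.2, SAP 8.1 and the Cox model in SAP 8.2.1(a), remove the p<0.10 screen, the AIC choice of coding and both open-ended confounder clauses from the treatment-effect models. Adjust only for M184V and CD4 at 350, as in Protocol 9.4.
- Pre-specify a fit that copes with separation, such as Firth penalised likelihood with profile-likelihood intervals for the odds ratio.
- Take any adjusted risk difference from a stratified method or an intercept-corrected Firth fit. Uncorrected Firth predictions are pulled towards 0.5. In 3,000 simulated trials with 5% true failure in both arms (M184V 40%, CD4 below 350 15%, both assumed), mean predicted failure was 6.1%, and the difference shifted by about 0.5 points in favour of DTG/RPV.
- Keep the candidate list, if wanted, as a descriptive table of factors associated with failure that does not feed the treatment estimate.
- State the same primary analysis in Protocol 9.4 and SAP 8.1.

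The cost is SAP wording and somewhat less analysis work, with no new data. If the unadjusted difference is named as primary, Protocol 9.4 changes too, and Protocol 9.9 routes major changes to the analysis through an amendment. The downside is that the exploratory screen no longer informs the treatment estimate.
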